### **4.2. Secondary Objectives and Hypotheses**

Secondary hypotheses for this trial are that cathflo activase supplementation for TSP:

1. Is safe
2. Does not inhibit pleurodesis
3. Reduces the incidence of recurrence of pleural effusion
4. Reduces the incidence of incomplete pleurodesis (presence of loculated effusions)
5. Shortens the time to achieve pleurodesis.
6. Does not increase pain associated with TSP
7. Improves the patient's subjective assessment of dyspnea
8. Does not prolong chest tube drainage or length of hospitalization
9. Is as cost-effective as TSP alone

Secondary objectives for this trial are:

1. To determine if giving cathflo activase with TSP is associated with a higher incidence of complications compared to TSP with placebo.
2. To determine if giving cathflo activase with TSP improves pleural fluid drainage compared to TSP with placebo.
3. To determine if giving cathflo activase with TSP is associated with a greater decline in serum Hemoglobin and/or incidence of blood transfusion compared to TSP with placebo.
4. To determine if giving cathflo activase with TSP is associated with an increased incidence of repeat pleurodesis compared to TSP with placebo.
5. To determine if giving cathflo activase with TSP is associated with a lower incidence of recurrence of pleural effusion compared to TSP with placebo.
6. To determine if giving cathflo activase with TSP is associated with a lower incidence of pleural fluid loculations compared to TSP with placebo.
7. To determine if giving cathflo activase with TSP is associated with a shorter time to RSP in patients with MPE compared to TSP with placebo.
8. To determine if giving cathflo activase with TSP is associated with a shorter time to RSP in patients with benign pleural effusion compared to TSP with placebo.
9. To determine if giving cathflo activase with TSP is associated with any difference in pain as measured by a standard visual analog pain scale compared to TSP with placebo.
10. To determine if giving cathflo activase with TSP is associated with any difference in scoring on a visual analog scale for measurement of dyspnea compared to TSP with placebo.
11. To determine if giving cathflo activase with TSP is associated with shorter duration of chest tube drainage compared to TSP with placebo.
12. To determine if giving cathflo activase with TSP is associated with a short length of hospital stay after TSP compared to TSP with placebo.

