13. To compare hospital costs associated with cathflo activase with TSP compared to TSP alone.

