## **9.0 STATISTICAL METHODS**

### **9.1. Primary and Secondary Outcome measures**

The primary outcome measure is the proportion of patients with successful pleurodesis at day 3 after administration of TSP. Successful pleurodesis is defined as “radiographically satisfactory pleurodesis” (RSP), as evidenced by 1) chest x-ray demonstrating similar or decreased amount of pleural fluid/opacification compared to day 0 (day pleurodesis is performed) and 2) drainage

of less than 100 ml of fluid over the preceding 24 hours. Chest x-ray results will be scored on a three-point scale (-1, 0, +1) based on comparison of pleural space opacification on the side of the TSP to baseline:

1. Worse (-1): Pleural space opacification is worse, suggesting residual undrained fluid or reaccumulation of loculated fluid.
2. Same (0): Pleural space opacification similar to baseline.
3. Better (+1): Pleural space opacification is better, suggesting less pleural fluid than at baseline.

The secondary outcome measures will include the following:

1. Proportion of patients with RSP at any time after TSP
2. Duration of chest tube drainage
3. Days to achieve RSP
4. Pain and dyspnea scores as assessed by a visual-analogue scale (on a scale from 0 to 100 mm, with a score of 0 indicating a complete absence of symptoms and a score of 100 maximum symptoms).
5. Proportion of patients requiring repeat pleurodesis
6. Proportion of patients requiring additional chest tube
7. Change in serum hemoglobin levels within three days of cathflo activase
8. Length of hospital stay (in days) after TSP.
9. All hospital costs associated with both treatment arms.

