## 9.2. Statistical Analysis Plan

Statistical summaries and analyses of data will be performed at MHS. Descriptive analysis will be performed for all data including means and standard derivation or medians for continuous variables and proportions for categorical variables. Comparison of outcomes between the two arms will be performed using t-test for numerical variables and Pearson  $\chi^2$ -test or Fisher's exact for categorical variables, and a one-sided p-value of 0.05 will be considered to be statistically significant.

The main analysis for primary outcome will be performed as per the intention-to-treat principle, and will include all the randomized participants with an observed outcome.(26) The primary outcome of the success rate of pleurodesis at day 3 will be analyzed using  $\chi^2$ -test. Time to symptomatic fluid recurrence following initial successful pleurodesis within 3 months follow-up period will be analyzed using a log-rank test. An interim analysis will be performed by the Memorial Healthcare System Quality and Safety Steering committee under [name] (currently officially the DSMB for MHS) after 50 patients are randomized in order to test for efficacy. The O'Brien-Fleming stopping rule will be used, which requires a P value of < 0.0088 (1-sided) for the primary outcome in order to stop at the interim analysis. The O'Brien-Fleming rule requires a P value of < 0.05 (1-sided) at the final analysis in order to declare a statistically significant difference in the primary outcome.(27) Analyses will be performed with the use of Prism 7.0 or SPSS 26 software.

Costs will be those related to study medications, initial hospital stay, and subsequent hospitalizations. All costs will be reported in US dollars and in 2020 prices. Cost data for both

arms will be obtained from MHS Strategic Financial Support Services. Outcomes will be measured in terms of probability of treatment success and/or complication, and utility of health states, which will be transformed to quality-adjusted life years (QALYs), calculated as the success rate of pleurodesis from each patient at day 3 after administration of TSP combined with pain and dyspnea scores.

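### Section 9.2 calls any outcome comparison significant at one-sided 0.05, with no gate, order, adjustment, exploratory label or test direction for 9 secondary outcome measures and 13 secondary objectives

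*Combined protocol and SAP*

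**What the plan says.** Section 9.1 names one primary outcome: "The primary outcome measure is the proportion of patients with successful pleurodesis at day 3 after administration of TSP". It then introduces a list with "The secondary outcome measures will include the following", which ends at item 9: "9. All hospital costs associated with both treatment arms". Pain and dyspnea share one item, so the list can also be counted as 10.

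Section 4.2 has a separate list under "Secondary objectives for this trial are", which ends at "13. To compare hospital costs associated with cathflo activase with TSP compared to TSP alone".

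Section 9.2 gives the general method, "Comparison of outcomes between the two arms will be performed using t-test for numerical variables" with chi-square or Fisher tests for categorical variables, and in the same sentence the threshold: "a one-sided p-value of 0.05 will be considered to be statistically significant". It adds one analysis that is not in the 9.1 list but is close to secondary objective 5: "Time to symptomatic fluid recurrence following initial successful pleurodesis within 3 months follow-up period will be analyzed using a log-rank test".

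The only control of the error rate is the O'Brien-Fleming rule in section 9.2, with one-sided 0.0088 at the interim and 0.05 at the end. It covers the primary outcome alone.

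**The concern.** This is a stated rule, not a silence. Read as written, a secondary comparison with a one-sided p-value below 0.05 is statistically significant, whether or not the primary outcome is positive and however many others were tried. Section 4.2 words the secondary items as hypotheses and as questions to be determined, which invites such statements.

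The direction of each test is also missing, and a one-sided p-value has no meaning without one. Objectives 1, 3 and 4 look for more complications, a larger fall in hemoglobin or more transfusion, and more repeat pleurodesis. Objectives 9 and 10 ask about pain and dyspnea in either direction. One undirected one-sided rule does not fit all of these.

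At stake is how the report will be read. The abstract says the trial aims to help develop the future standard of management, and section 12.0 plans publication. A label of significance on hospital stay, drainage time or recurrence could carry weight even after a negative primary result.

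**Working it through.** **Inputs from the documents.** Threshold: one-sided 0.05 (9.2). Number of secondary tests: 9 outcome measures, or 10 with pain and dyspnea split (9.1); 13 objectives (4.2). The documents state no error rate for the secondary family, so there is no planned figure to reproduce for that quantity.

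**The plan's own sample size.** With 60% against 80%, one-sided 5%, 80% power (6.1) and pooled variance under the null hypothesis:

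n per arm = [1.645·√(2·0.7·0.3) + 0.842·√(0.6·0.4 + 0.8·0.2)]² / 0.20² = 63.9, so 64.

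Allowing for 5% loss: 64/0.95 = 67.4, so 68 per arm and 136 in total. This matches section 6.1. The size rests on the primary outcome alone.

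**Independent tests.** The chance of at least one p-value below 0.05 among k tests with no true effect is 1 − 0.95^k:

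- k = 9: 1 − 0.95^9 = 37.0%
- k = 10: 1 − 0.95^10 = 40.1%
- k = 13: 1 − 0.95^13 = 48.7%; expected number of false results 13 × 0.05 = 0.65

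**Correlated tests.** The outcomes overlap. Under section 8.3, meeting both criteria on day 3 leads to removal of the chest tube, which ties time to RSP to drainage duration and plausibly to stay and cost. Take normal test statistics with a common correlation r. The documents give no value for r, so it is assumed. With c = 1.645,

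chance = 1 − ∫ φ(u)·Φ[(c − √r·u)/√(1 − r)]^k du.

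| Tests | r = 0 | r = 0.3 | r = 0.5 | r = 0.7 | r = 0.9 |
|---|---|---|---|---|---|
| 9 | 37.0% | 28.8% | 23.3% | 17.7% | 11.2% |
| 10 | 40.1% | 30.7% | 24.7% | 18.5% | 11.6% |
| 13 | 48.7% | 35.8% | 28.1% | 20.6% | 12.4% |

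At r of 0.3 to 0.5 the range is 23.3% (9 tests) to 35.8% (13 tests). Even at r = 0.9 it stays above 5%.

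**Direction.** Of the 13 objectives, seven are worded as benefit (2, 5, 6, 7, 8, 11, 12), three as harm (1, 3, 4), two as a difference either way (9, 10), and one compares costs without a direction (13). For the seven benefit objectives alone, the chance of at least one false benefit is 1 − 0.95^7 = 30.2% if independent, and 24.5% to 20.3% at r = 0.3 to 0.5.

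**The case against.** Leaving secondary outcomes unadjusted is common. The plan does single out the primary: one outcome, the sample size built on it, and its own interim and final thresholds. This stands, and it means that the primary conclusion is not put at risk by this gap. It does not answer the point, because the plan goes beyond leaving the secondary results unadjusted: it says in advance that they will be called significant.

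Three stronger readings are tempting and are not supported.

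- A reader might infer a flat 49% chance of a false result. That needs 13 mutually independent tests, and the protocol's own tube-removal rule links several of them. Section 9.1, the more natural list for a comparison of outcomes, has 9 items. Complications and transfusion may also be rare, and Fisher's exact test on rare events has a true error below 0.05.
- A reader might infer that the report will probably show a false benefit. Only seven objectives are worded as benefit, and their figure is about 20% to 30%.
- A reader might add separate tests of pain and dyspnea at each visit and reach about 70%. Sections 8 and 8.2 describe when these scores are collected; no section says that each visit will be tested. The absence of a stated analysis time is a gap in the plan, but it does not create a planned set of tests.

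The common-correlation model is a simplification in the other direction too. Objectives 7 and 8 concern different patients, so those two tests are independent. A harm-directed test can be negatively correlated with a benefit-directed one.

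**Conclusion.** The point holds as a gap in the rule for secondary outcomes. With no drug effect, the chance of at least one false significant secondary result is roughly 23% to 36%, assuming 9 to 13 tests and a common correlation of 0.3 to 0.5, and about 37% to 49% under independence. The count depends on whether the 9.1 or the 4.2 list is taken as the family, which the plan does not say. These are chances of a false result in whatever direction each test takes, so they are not chances of a false claim of benefit. The missing directions are a separate defect in the same sentence and do not depend on any assumed correlation. Label: cheap improvement.

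**What to change.** In section 9.2, replace the general significance sentence with text to this effect: *Statistical significance will be declared for the primary outcome only, using its separate interim and final thresholds. Secondary and safety outcomes will be reported as between-arm differences with two-sided 95% confidence intervals, labelled as not adjusted for multiplicity, without statements of significance.*

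If the sponsor wants one secondary claim, name that outcome and the direction of its test in advance, and test it only if the primary outcome is significant.

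Two-sided intervals also suit the harm objectives and those that ask about a difference either way, so the missing directions no longer matter for them. The cost is that the sponsor gives up significance labels on secondary outcomes. The sample size of 136, the procedures and the data collected do not change.

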## 5.0. STUDY DESIGN

The SPIRIT (Standard Protocol Items for Randomized Trials) recommendations were followed in preparing this protocol.(20,21) The study is a single center, prospective, randomized, double-blind, placebo-controlled trial with two arms to compare the successful pleurodesis rates and potential complications after TSP with or without cathflo activase in patients with recurrent pleural effusion.

This study is designed as a single center study at MHS with two study sites, although it may be made available to thoracic surgery programs at other institutions to consider opening as a collaborative effort to accelerate patient accrual. All patients for whom bedside chemical pleurodesis is planned will be considered eligible for the study regardless of effusion etiology. Chest X-ray and chest tube insertion will be performed in all consented participants, and the drained pleural fluid amounts will be recorded and, if not done before enrollment, sent for chemical, bacteriological and cytological evaluation. Then the participants will undergo stratified randomization according to effusion etiology (malignant vs. non-malignant) with the use of a computer-based system in a 1:1 ratio. TSP with cathflo activase or placebo will be administered through the chest tube immediately after randomization. The trial will be conducted on a double-

blind basis and therefore participants and the clinician will be unaware of each participant's allocated treatment group.

Additional centers may be invited to participate, in which case the IRB will be notified if other programs decide to open the protocol at other sites.

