### **6.3. Randomization**

Subjects undergoing pleurodesis as part of their standard of care treatment, and who have signed informed consent, will undergo a stratified randomization according to effusion etiology (malignant vs. non-malignant) with the use of a computer-based system in a 1:1 ratio. A statistician will randomly generate treatment allocation codes (randomization lists for either placebo or cathflo activase) according to study design specifications as determined by the statistician and principal investigator. The treatment allocations will be given to pharmacy with sealed opaque envelopes. Once a subject has consented to enter the trial and is ready for pleurodesis an envelope will be opened and an independent pharmacist (researcher) will prepare the drug or placebo in a syringe labeled with “study drug” and the randomization code according to the treatment allocations. Syringes containing placebo or cathflo activase (study drug) cannot be distinguished because both preparations are clear and colorless and have the same volume. The prepared syringe labeled “study drug” will be brought to the bedside by the pharmacist and nurse and the subject will then be given the allocated treatment regimen. The subject’s ID, date, time and randomization code will be recorded. The doctor/nurse and subject will not know which drug was injected (double blinded). The preparer (pharmacist) will retrieve the recorded information, determine if the injection was done as planned, and save the documents in a secured place.

The envelopes should be opened just after the subject has consented to enter the trial and is ready for pleurodesis. In case of a broken or lost syringe, the preparer will use the allocation code of the envelope and the allocation log to determine whether the syringe should be replaced with placebo or study drug.

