## 8.2. Assessments/Tasks

Following consent, a baseline assessment will be undertaken pre-randomization by a member of the trial team and entered into the REDCap system hosted at Office of Human Research of MHS. The following data will be recorded prior to randomization:

1. Patient demographics and physical characteristics
2. Mode of presentation, current diagnosis, cause of effusions (if known).
3. Medical history and current medication.
4. Previous pleural interventions.
5. Symptoms, including pain and SOB according to a visual analog scale (VAS) (Appendix I, II).
6. Pleural fluid biochemical and cytological test results
7. Baseline hemoglobin (day of or day before TSP)
8. Baseline (day of or day before TSP) CxR and chest CT (if available) findings.

After randomization and TSP with or without cathflo activase, all patients will have daily follow-up until the chest tube is removed, and at 14 and 28 days, and three months after TSP. At all visits, the following data will be recorded:

1. VAS for chest pain and SOB will be documented (Appendix I, II).
2. CxR (PA and lateral preferred).
3. Drained pleural volumes in 24 hours (if the chest tube is still in place).
4. Serum hemoglobin (only for inpatient visits within three days of the pleurodesis procedure).
5. Repeat pleural interventions.
6. Chest CT scan, as justified by the principal investigator.

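### Efficiency only: the section 9.2 tests ignore the etiology stratum used at randomisation and do not use baseline VAS or hemoglobin as covariates

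*Combined protocol and SAP*

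**What the plan says.** - **Randomisation.** Section 5.0 says that "participants will undergo stratified randomization according to effusion etiology (malignant vs. non-malignant"; section 6.3 repeats it: patients "will undergo a stratified randomization according to effusion etiology (malignant vs. non-malignant". The ratio is 1:1. No block size is given.
- **Baseline data.** Section 8.2 lists pain VAS, dyspnea VAS and hemoglobin among the items recorded before randomisation. The cause is listed there as "cause of effusions (if known". Section 5.0 has the drained fluid, "if not done before enrollment, sent for chemical, bacteriological and cytological evaluation".
- **Primary test.** Section 9.2: "The primary outcome of the success rate of pleurodesis at day 3 will be analyzed using" a chi-square test. The same outcome is tested after 50 patients under a rule "which requires a P value of < 0.0088 (1-sided) for the primary outcome in order to stop at the interim analysis", and at the end against one-sided 0.05.
- **Other tests.** Section 9.2: "Comparison of outcomes between the two arms will be performed using t-test for numerical variables". Time to symptomatic recurrence after an initially successful pleurodesis, "within 3 months follow-up period will be analyzed using a log-rank test".
- **Outcome definitions.** Section 9.1 defines the hemoglobin outcome as a change. It lists pain and dyspnea scores without a time point, and without saying whether the score or its change is compared.

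**The concern.** A factor chosen for stratification is usually one expected to predict outcome. If etiology predicts radiographically satisfactory pleurodesis (RSP), a test that ignores it leaves between-stratum variation in the error term and gives up some power that the same patients could supply. Likewise, a t-test on follow-up VAS, or on change in hemoglobin, is usually less precise than ANCOVA on the recorded baseline. That matters most for the secondary questions of pain and hemoglobin decline (section 4.2), where an imprecise comparison can look falsely reassuring. At stake is precision. Bias and the validity of the primary conclusion are not in question.

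**Working it through.** **1. The plan's sample size.** Inputs from section 6.1: 60% versus 80% RSP, one-sided 5%, 80% power, 5% loss. With the pooled-variance formula and no continuity correction:

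n per arm = [1.645·√(2·0.70·0.30) + 0.842·√(0.60·0.40 + 0.80·0.20)]² / 0.20² = (1.0660 + 0.5323)² / 0.04 = 63.9

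63.9 / 0.95 = 67.2, rounded up to 68 per arm, or 136 in total. This matches.

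**2. Assumptions for the comparison.** The documents give neither the malignant share nor RSP rates by etiology. Assumed:
- malignant share 30% to 85%;
- control RSP lower in malignant effusions by 0, 12.5, 25 or 37.5 points;
- overall rates held at 60% and 80%, with a common odds ratio;
- 128 evaluable patients (64 per arm) at the end and 50 at the interim look;
- exact balance, blocks of 4, or unrestricted 1:1 allocation within strata.

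The comparison is by simulation: signed pooled chi-square versus CMH, both one-sided without continuity correction.

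**3. Power, stratified minus unstratified, in percentage points.**

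| Gap in control RSP | Final power (limit 0.05) | Crossing 0.0088 at 50 patients |
|---|---|---|
| 0 | -0.5 to -0.1 | -1.0 to -0.5 |
| 12.5 | -0.2 to +0.2 | -0.8 to -0.2 |
| 25 | +0.3 to +1.5 | -0.3 to +1.2 |
| 37.5 | +0.8 to +3.9 | +0.5 to +3.6 |

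The unstratified chance of crossing at 50 patients is 18.6% to 20.5%. Gains are largest near a 45% malignant share and smallest at 85%. As a single case, with a 50% share and exact balance, final power is 81.0% versus 81.5% at a 20-point gap and 82.3% versus 85.1% at 40 points. If 20% of malignant effusions are entered as non-malignant, the gain over both looks falls from about +0.3 to +1.4 to 0.0 to +0.8 (25-point gap), and from about +1.0 to +3.5 to +0.2 to +2.3 (37.5-point gap).

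**4. Type I error.** When strata are balanced, the pooled test overstates the variance. At a 50% share and a 40-point gap, the between-stratum part is 0.5·0.5·0.40² = 0.04 of a total 0.60·0.40 = 0.24. The true variance is then 0.20/0.24 = 0.83 of the assumed one, and the effective critical value is 1.645/√0.83 = 1.80, a one-sided size of about 3.6%. Simulation gives 3.4%, against 4.9% for CMH. Over both looks, with limits 0.0088 and 0.05:
- blocks of 4, gaps of 25 to 37.5 points: about 3.9% to 4.9% unstratified, about 5.3% to 5.6% with CMH;
- no gap, or unrestricted allocation: about 5.1% to 5.7% for both tests.

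At the final look alone, CMH size is 4.6% to 5.2%, apart from 5.4% at an 85% share, a 37.5-point gap and exact balance.

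**5. Baseline adjustment.** Let r be the baseline-to-follow-up correlation, with equal variances. Relative to a raw score (variance 1), a change score has variance 2(1-r) and ANCOVA 1-r². The ANCOVA saving is therefore r² against a raw score and 1-(1-r²)/[2(1-r)] = (1-r)/2 against a change score.

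| r | Saving against raw VAS score | Saving against change (hemoglobin) |
|---|---|---|
| 0.3 | 9% | 35% |
| 0.5 | 25% | 25% |
| 0.7 | 49% | 15% |
| 0.9 | not tabulated | 5% |

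The documents give no r. If VAS is compared as a change, the right-hand column applies to it too.

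**The case against.** The strongest reply is that nothing here is wrong and the primary gain may be nil. The unstratified test keeps at least 80% final power in every case examined, gaps up to 12.5 points give essentially no gain, and gains above 1.5 points appear only at 37.5. All of that stands, and it keeps the point minor.

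The ranges also depend on a common odds ratio. If only malignant effusions benefit (60% share, 25-point gap), the two-look gain is -0.1 to +0.1 points, against +0.9 to +1.4 under a common odds ratio. If only non-malignant effusions benefit (30% share, same gap), it is +3.9 to +6.2. The ranges are therefore not bounds. The interim figures further treat 50 randomised patients as 50 with an outcome.

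A second reply is that CMH removes conservatism that keeps the planned test under 5% when strata are balanced and etiology is prognostic. That is true and belongs among the costs. A reader might infer that stratifying inflates type I error. It does not: the excess comes from leaving the final limit at 0.05 after an earlier look, and the planned test shows the same excess with no gap or with unrestricted allocation.

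Third, the log-rank comparison covers only patients whose pleurodesis first succeeded, a group formed after randomisation, so balance within strata is not assured. That stands. Stratifying that test is optional, and no gain is claimed for it.

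**Conclusion.** The point holds as a low-cost improvement of minor weight. Section 9.2 uses neither the randomisation stratum nor a baseline covariate. For the primary outcome the likely effect on final power runs from a loss of up to 0.5 points to a gain of up to 3.9, depending on how far etiology predicts RSP, and the gain shrinks if etiology is misclassified. Gains for VAS and hemoglobin may be larger, but they depend on correlations that the documents do not give.

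Three stronger readings are not supported:
- That an unstratified test after stratified randomisation is invalid or inflates error. It is unbiased, and at a single look its size is at or below about 5%.
- That the trial is too small. The figure of 136 reproduces.
- That baseline hemoglobin is unused, or that etiology is absent from the plan. Baseline hemoglobin enters by subtraction, and secondary objectives 7 and 8 in section 4.2 compare time to RSP within each etiology, to which the default t-test applies.

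**What to change.** In section 9.2:
1. Make the primary test a one-sided CMH test without continuity correction, stratified by etiology as entered at randomisation and not reclassified later, and use it at both looks. Report the Mantel-Haenszel risk difference with its confidence interval. Keep the unstratified chi-square as a sensitivity analysis.
2. Analyse pain VAS, dyspnea VAS and hemoglobin by ANCOVA with the baseline value and the stratum as covariates, at a named time point (for example day 3, to match the primary outcome).
3. As a supporting detail, state which stratum a patient of unknown cause is entered in.
4. Optionally, stratify the log-rank test by the same factor.

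**Cost.** Wording only: no new patients, visits or measurements, and 136 stands. If etiology is not prognostic, the price is up to 0.5 points of final power and up to 1.0 point of the chance of crossing at 50 patients. With balanced strata and a prognostic etiology, the plan should also acknowledge the overall type I error of about 5.3% to 5.6% under the present limits. Correcting the final limit for the interim look would address that and is a separate change. The choice of test should be settled before the 50-patient look.
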